3.3.5 Phase 2 Lung Cancer Study [REDACTED]

OTL38 injection was evaluated in 100 subjects dosed with 0.025mg/kg with known or suspected lung cancer. [REDACTED]

A summary of safety findings from this study is as follows:

- Most subjects in the Safety population (94/100) had at least one TEAE during the study.
- Study drug infusion was interrupted in 20/100 subjects due to study drug-related AEs (mild-moderate infusion reaction, nausea, vomiting). Infusion was not restarted for 6 subjects with infusion related AEs that were considered related to study drug. These subjects were discontinued from the study. Most AEs resolved the same day.
- The most common TEAEs occurring in subjects were procedural pain (50/100; 50.0%), nausea (33/100; 33%), cough (29/100; 29%), incisional site pain (20%), vomiting (17/100; 17%) pneumothorax (17/100; 17%).
- Most subjects reported TEAEs of grade 2 (moderate) severity (41/100; 41%). Grade 1, grade 3, grade 4 TEAEs were reported by 24%, 25% and 4% of subjects, respectively.
- Most of severe or life-threatening TEAEs were due to post-surgical pain (4/29; 13.8%); hypertension (4/29; 13.8) and pneumonia (3/29 10.3%).
- There were 20 (20%) subjects with a study drug-related TEAE. [REDACTED]

[REDACTED]

- With the exception of the 20 infusion reactions, all TEAEs were typical of those anticipated in the subject population undergoing this type of surgical procedure.
- There were no TEAEs that were considered related to the imaging system.
- There were 14 (14%) subjects with SAEs, none of which were related to study drug. The type and frequency of SAEs was considered consistent with the underlying disease status and medical history of the subjects.
- No subject died during the study.

3.3.6 Other Clinical Experience in Lung and Pituitary Cancer:

[REDACTED]

Please refer to the Investigator’s Brochure for more detailed information on OTL0038 and OTL38 Injection.

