2.3 Exploratory Objectives

2.4 Safety Objectives

1. To assess the safety and tolerability of single intravenous doses of OTL38.
2. To assess the safety of the Fluorescence Imaging Systems for intraoperative imaging when used with OTL38.

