If a subject experiences more than 1 AE within system organ class or preferred term, that subject will be counted only once for that event under the maximum severity or most related category within the relevant category. In the event that the relationship to study drug or the severity of the event is missing, for tabulation purposes the maximum relationship will be assumed, and a Grade 3 (Severe) level of severity will be assumed.

Adverse Events of Special Interest (AESIs) will be captured and analyzed. An AESI is defined as an infusion related reaction and will be identified through the following mechanisms to include all AEs that meet the following criteria:

- AE that are not considered procedural in nature (Procedural complications and administration related problems will be excluded and defined as any AE with a preferred term of “procedural complication” or “infusion site discomfort” will be excluded.)

AND meets at least one of the following:

- AE that resulted in interruption of study drug infusion in the study drug administration data (study drug administration CRF; was infusion interrupted = yes; reason for interruption = AE)
- AE that resulted in study drug interruption or study drug withdrawal in the AE data (all AEs with an action taken with study drug = drug interrupted, or drug withdrawn)
- AE that started during the study drug infusion as per the recoded start time (AEs with a start date of Study Day 1 AND a start TIME within the infusion window as defined as start time >

infusion start time and \leq infusion stop time; AEs that have the same start time as the study drug infusion will not be counted)

- AE presumed to start during the study drug infusion as per the recorded start/stop dates and assigned relatedness (AEs without a recorded start time, that have both a start date and stop date of Study Day 1, and are indicated as Related or Possibly Related for their relationship to OTL38 Infusion)
- AE that started during the study drug infusion as per the recorded start time which abated after infusion being stopped or reduced.

Incidence of TEAEs will be summarized by age group, race, and gender if there are sufficient numbers of subjects within these subgroups. Otherwise only line listings will be provided.

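### The AESI rule for infusion related reactions drops a drug-related AE timed just after a completed infusion, yet counts the same AE if its start time is blank

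*SAP*

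**What the plan says.** SAP 14.3 states: "An AESI is defined as an infusion related reaction and will be identified through the following mechanisms to include all AEs that meet the following" (the list of conditions comes next). AEs regarded as procedural are removed first. An AE then qualifies by meeting any one of five routes, numbered here in the order the SAP lists them:

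1. "AE that resulted in interruption of study drug infusion in the study drug administration data".
2. Interruption or withdrawal recorded on the AE form: "all AEs with an action taken with study drug = drug interrupted, or drug withdrawn".
3. Timed onset, dated Study Day 1, with "a start TIME within the infusion window as defined as start time" later than infusion start and not later than infusion stop. Relatedness plays no part.
4. Untimed onset: "AEs without a recorded start time, that have both a start date and stop date of Study Day 1, and are indicated as Related". A score of Possibly Related also suffices. The SAP presents this as a presumption that onset fell within the infusion.
5. Recorded onset during the infusion, with abatement once it was stopped or slowed.

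Protocol 5.6.4 gives an infusion of about 60 minutes. On earlier experience, Protocol 3.3.5 reports: "Study drug infusion was interrupted in 20/100 subjects due to study drug-related AEs". The first safety objective in SAP 2.4 is: "To assess the safety and tolerability of single intravenous doses of OTL38".

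**The concern.** The AESI is named for its relation to the infusion, but for timed events the rule tests only whether onset coincided with the infusion. Nausea or a hypersensitivity event that begins a few minutes after an uninterrupted infusion and is judged Related is left out. If the site leaves the time blank and the event resolves that day, it is included. Better documentation thus removes an event that poorer documentation would keep, and routine data cleaning can change the count.

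What is at stake is how the known drug risk is displayed. Infusion reactions are the drug-related finding that Protocol 3.3.5 singles out from Phase 2, and they are the only AESI in the SAP. A reader of the AESI table will take it as the frequency of infusion related reactions. It should not turn on whether a time field was completed.

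**Working it through.** The documents state no figure that depends on this rule, so there is none to reproduce. The check has two parts.

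**Part 1: test events run through the rule.** Take a non-procedural AE and an uninterrupted infusion from minute 0 to minute 60 on Study Day 1, with no interruption or withdrawal recorded on the AE form. Routes 1 and 2 are then not met. Route 5 requires recorded onset during the infusion, so it cannot admit a later onset. Routes 3 and 4 decide.

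| Recorded start | Stop date | Relationship | AESI? |
|---|---|---|---|
| Minute 1 to 60 | Day 1 or 2 | Related | Yes (route 3) |
| Minute 1 to 60 | Day 1 or 2 | Not Related | Yes (route 3) |
| Minute 61 or 90 | Day 1 or 2 | Related | No |
| Missing | Day 1 | Related | Yes (route 4) |
| Missing | Day 2 | Related | No |
| Missing | Day 1 | Not Related | No |

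Possibly Related is treated as Related in route 4 and makes no difference in route 3.

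Three things follow:
- A Related AE at minute 61 that resolves on Day 1 is excluded, while the same AE without a time is included.
- The blank-time half holds only if the AE also ends on Study Day 1 and is scored Related or Possibly Related.
- Route 3 admits AEs scored Not Related, so the rule can also add events that are not reactions to the drug.

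**Part 2: scale.** The inputs are:
- Phase 2 subjects with infusion interrupted for drug-related AEs: 20/100 (Protocol 3.3.5).
- Phase 2 subjects with a drug-related TEAE: 20/100 (Protocol 3.3.5).
- Planned size: up to about 130 (Protocol synopsis).

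An AE that caused an interruption meets route 1 or 2 whatever its recorded time. The subjects at risk of being missed are those with a drug-related TEAE but no interruption. If the two groups of 20 are the same people, their number is 20 − 20 = 0 of 100.

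The exact (Clopper-Pearson) two-sided 95% upper limit for 0/100 is 1 − 0.025^(1/100) = 0.0362, or 3.6%. Applied to the planned size, 0.0362 × 130 = 4.7 subjects. For comparison, the Phase 2 rate of 20% corresponds to 0.20 × 130 = 26 subjects.

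**The case against.** The strongest reply is that this is a small gap in a descriptive display.

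- **No event disappears.** A related AE with later onset stays in the TEAE tables by severity and by relationship to drug, and in the listings. SAP 14.3 also allows an optional description by time of onset. AESI is not among the safety endpoints in SAP 12.4, and no visible test or decision depends on the count. This stands and limits the importance of the point, but it does not put the event back into the AESI table.
- **Route 4 is a deliberate presumption for missing data.** It fits the same section's practice of assuming the strongest relationship when that field is blank. This stands in that the routes do not contradict each other in words. The difficulty is the result: identical reactions are classified by completeness of recording. The documents do not show that start times are often missing or differ by site, so how often this would happen is unknown.
- **Route 5 is not wholly redundant.** It is not tied to Study Day 1, and Protocol 5.8.1.2 allows infusion on the day before surgery. This is true, but it still needs onset during the infusion.
- **Redaction.** Text is blacked out near the infusion instructions (Protocol 5.6.4) and in the risk discussion (Protocol 3.4.1). A reason for the window may lie there and cannot be judged.

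A reader might infer that a share of the Phase 2 rate of 20% would go uncounted. The documents do not support this: those 20 subjects had their infusion interrupted, so route 1 or 2 would capture them. A reader might also infer that the rule biases the AESI count in the drug's favour. That is not established either, because route 3 counts unrelated AEs during the infusion. Only for related AEs timed after a completed infusion is the direction fixed, and there it is an undercount.

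**Conclusion.** The point holds as a modest flaw in the definition of the only AESI. For an uninterrupted infusion, a Related or Possibly Related AE recorded as starting after infusion stop meets none of the five routes. The same AE with a blank start time counts if it starts and stops on Study Day 1. This follows from the text alone.

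The size is unknown and probably small. If the two Phase 2 groups of 20 are the same people, the subject-level loss there was 0/100, with an upper limit of 3.6% or about 4.7 of 130. The equal counts suggest the overlap, but Protocol 3.3.5 does not state it. Carrying the limit over also assumes that reactions occur and are recorded in this trial as they were in Phase 2. The net direction of error across all timed AEs remains open.

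**What to change.** Amend SAP 14.3 as follows:

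1. Add a route for non-procedural AEs judged Related or Possibly Related whose recorded onset falls after infusion stop on the calendar day of infusion.
2. Use the same stop-date condition for this route and for untimed AEs: either keep resolution on the day of infusion for both or drop it for both. Otherwise a related AE lasting into the next day would count if timed and not if untimed.
3. Show the AESI table in three rows plus a total, with each subject counted once in the total: (a) interruption or withdrawal, or recorded onset during infusion; (b) no start time, presumed during infusion; (c) recorded onset after infusion stop. Rows (a) and (b) together keep the count under the SAP's present definition visible. If the stop-date condition is dropped, footnote how many untimed AEs enter only for that reason.

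The cost is SAP wording, through the documented amendment that SAP section 1 provides for, and a few lines of programming on data the rule already uses. The downside is that some same-day perioperative events scored Possibly Related may enter row (c). Nausea (33/100) and vomiting (17/100) were common TEAEs in Phase 2. The separate row keeps such events identifiable.

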14.4 Deaths, Serious Adverse Events and Adverse Events

Treatment-emergent serious AEs (SAEs), TEAEs leading to early study withdrawal, and TEAEs resulting in death (included in the serious definition) will be summarized for all subjects in the SfAS. Summary tables will reflect the number and percentage of subjects experiencing at least 1 TEAE in each system organ class and preferred term within each AE subset (serious, leading to early study withdrawal, or death). In addition, the number of subjects experiencing any TEAE in the respective subset will be reported.

Adverse events leading to early study withdrawal, AEs resulting in death, and SAEs will also be presented in data listings.

14.5 Clinical Laboratory Evaluations

The analysis of laboratory parameters will include descriptive statistics for the baseline and all post-baseline visits as well as the changes from baseline at each visit. Baseline distributions and shifts from baseline to each post-baseline study visit for categorical lab parameters will also be provided. Where relevant, as noted above, changes from baseline summaries will include a change from screening to pre-infusion.

Urinalysis data will not be summarized but will be provided in a data listing. For all relevant laboratory data, values above or below normal limits will be flagged along with the direction of abnormality in line listings.

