
Eligibility Criteria
	
Inclusion:
 
 1. Male and Female subjects 18 years of age and older 2. Have a primary diagnosis, or a high clinical suspicion, of cancer in the lung warranting surgery based on CT/PET or other imaging 3. Are scheduled to undergo surgical thoracoscopy for diagnostic wedge resection followed by anatomic lung resection 4. Female subjects of childbearing potential or less than 2 years postmenopausal agree to use an acceptable form of contraception from the time of signing informed consent until 30 days after study completion 5. Ability to understand the requirements of the study, provide written informed consent and authorization of use and disclosure of protected health information, and agree to abide by the study restrictions and to return for the required assessments 
Exclusion:
 
 1. Previous exposure to OTL38 2. Any medical condition that in the opinion of the investigators could potentially jeopardize the safety of the subject 3. History of anaphylactic reactions to folate, including synthetic folic acid (pteroylmonoglutamic acid) and contrast agents containing indocyanine green for near infrared imaging. Subjects with a medical history of ‘idiopathic anaphylaxis’ will require evaluation. 4. History of allergy to any of the components of OTL38, including folic acid 5. A positive serum pregnancy test at Screening or a positive urine pregnancy test on the day of surgery or day of admission for female subjects of childbearing potential 6. Clinically significant abnormalities on electrocardiogram (ECG) at screening. 7. Presence of any psychological, familial, sociological condition or geographical challenges potentially hampering compliance with the study protocol and follow-up schedule 8. Impaired renal function defined as eGFR < 50 mL/min/1.73m² 9. Impaired liver function defined as values > 3x the upper limit of normal (ULN) for alanine aminotransferase (ALT) or aspartate aminotransferase (AST), alkaline phosphatase (ALP), or >2x ULN for total bilirubin except in subjects with Gilbert’s syndrome. 10. Received an investigational agent in another investigational drug or vaccine trial within 30 days prior to the administration of study drug 11. Known sensitivity to fluorescent light

Number of Subjects
	
Up to approximately 130 subjects

Number of Investigator Sites
	
Up to approximately 15 investigational sites

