3.2 Rationale

Approximately 85% of lung and pleural malignancies express folate receptor positive nodules (FR+), thus making folate receptors (FR) ideal targets for imaging agents such as OTL-38 (Shen 2015). OTL38 has been observed in preliminary Investigator Initiated studies as being effective in identifying non-malignant lung nodules. These nodules (such as granulomas) do not necessarily pose a threat to the patient's life, but are still targeted for removal by a surgeon to confirm the absence of cancer. Both malignant adenocarcinoma and benign lung nodules that fluoresce in situ are noted to have infiltrates of tumor associated macrophages (TAMs) expressing FR on immunohistochemistry (De Jesus 2015, Shen 2015). Therefore, this intraoperative imaging of lung cancers and nodules would be well-suited in the reduction of positive margins, identification of synchronous lesions, localization of sub-centimeter nodule and tumor tissue, and potentially improving clinical outcomes in these patients. Chemotherapy does not appear to affect FR expression in cancer specimens as examined by immunohistochemistry thus prior treatment is unlikely to affect utility of FR ligands as imaging agents (Crane 2012, Okusanya 2014). Since FR α is normally expressed only in the proximal tubules of the kidneys and in the choroidal plexus, uptake of OTL0038 in the kidneys is possible (Ross 1994). However, the imaging described in this protocol will not involve tissue proximal to the kidneys.

While folate will initially distribute to all cells, redistribution, metabolism, and excretion will eliminate most of this agent from healthy tissues within 2-3 hours. Tumor cells that over expresses FR will retain folate and any fluorescent labeled folate conjugate (Leamon 1993). On Target Laboratories, Inc. has developed OTL0038, a folate analog ligand conjugated with an indole cyanine green-like dye developed by On Target Laboratories, Inc. as a tumor-imaging agent for patients with tumors that overexpress FR.

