In addition, shift tables (i.e., low-normal-high at baseline versus low-normal-high at last visit) will be provided where appropriate. Urinalysis and pregnancy results will not be summarized but will be provided in a data listing. For all relevant laboratory data, values above or below normal limits will be flagged along with the direction of abnormality in line listings.

8.2.5.4.3 *Vital Signs*

Vital signs will be summarized via descriptive statistics similar to that described above for clinical laboratory evaluations with regard to changes from baseline.

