6 SAMPLE SIZE DETERMINATION

7 GENERAL ANALYSIS AND REPORTING CONVENTIONS

The following general analysis and reporting convention will be applied for this study:

- For analysis purposes, baseline will be defined as the last recorded non-missing observation prior to exposure to study drug.

Categorical variables will be summarized using counts (n) and percentages (%) and will be presented in the form “n (xx.x)”. Percentages will be based on the relevant total category count excluding missing data if not otherwise mentioned. To ensure completeness, where relevant, summaries for categorical and discrete variables will include all categories, even if no subjects had a response in a particular category. When the statistical methods use the term “proportion” to describe the calculation of a statistic it is understood that the proportion may be transformed into a percentage for the purposes of data presentation unless otherwise stated.

Continuous variables will be summarized using mean, SD, minimum, maximum, median, and number of subjects. The mean and median will be reported to one more level of precision than the original observations, and the SD will be reported to 2 more levels of precision than the original observations. The minimum and maximum will be the same precision as the original data.

For tests of hypotheses, the associated p-value and confidence interval (CI) will be reported, where applicable. All p-values will be rounded to 3 decimal places; p-values that round to “0.000” will be presented as “<0.001”.

Dates will be displayed as ddmmmyyyy (e.g., 24Jan2005).

Age (in years) will be calculated using the date of birth and the date of informed consent as (date of informed consent – date of birth) / 365.25.

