12.3 Exploratory Endpoints

12.4 Safety Endpoints

Safety analyses will be conducted using the SfAS.

1. Incidence rates of treatment-emergent adverse events (TEAEs) defined as adverse events (AEs) starting, or worsening, on or after exposure to study drug. See Section 7.1 of the protocol.
2. Incidence rates of Adverse Device Effects (ADEs) defined as any untoward and unintended response to a medical device, in this study, the camera/imaging system. See Section 7.2.1 of the protocol.
3. Summary statistics for chemistry and hematology parameters. Urinalysis results will be presented in line listings only.
4. Summary statistics for vital signs.
5. Summary statistics for physical examination results.
6. Summary statistics for Electrocardiograms (ECGs).

7. Pathology and Immunohistochemistry results will be included in line listings only.
8. Summary statistics for on and off times overall imaging systems and for each imaging system will be provided. Data will also be presented in line listings.
9. Pregnancy test results will be presented in line listings only.
10. Incidence rates for concomitant medications defined as all medications started, or continuing, during or after exposure to study drug. Prior medications will be presented in line listings only. See Section 5.7 of the protocol.

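### No planned laboratory table counts subjects whose liver tests worsen from a baseline that is already raised but still eligible

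*SAP*

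**What the plan says.** - **Entry.** Exclusion 9 (Protocol synopsis and 5.2.2) reads "Impaired liver function defined as values > 3x the upper limit of normal (ULN) for alanine aminotransferase (ALT" and goes on to AST and ALP at the same limit. For total bilirubin the limit is 2x ULN, with an exemption for Gilbert's syndrome. Values above normal but within these limits are therefore eligible.
- **Protocol analysis.** Section 8.2.5.4.2 plans changes from baseline and shifts for categorical parameters. As a further item it adds that "shift tables (i.e., low-normal-high at baseline versus low-normal-high at last visit) will be provided where appropriate".
- **SAP analysis.** Section 14.5 plans "descriptive statistics for the baseline and all post-baseline visits as well as the changes from baseline at each visit" and says that "shifts from baseline to each post-baseline study visit for categorical lab parameters will also be provided". It does not define categorical and does not mention the low-normal-high table. Listings flag out-of-range values by direction only. SAP 12.4 describes the endpoint as "Summary statistics for chemistry and hematology parameters. Urinalysis results will be presented in line listings only".
- **Statistics reported.** SAP 7: "Continuous variables will be summarized using mean, SD, minimum, maximum, median, and number of subjects".
- **Adverse event route.** Under Protocol 7.3.2, a laboratory abnormality judged clinically significant is reported as an AE, alone or within a clinical syndrome. SAP 12.4 counts events that start or worsen after exposure. SAP 14.3 tabulates them by preferred term and maximum severity.

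**The concern.** Liver injury, if it occurred, would be expected in a few outlying subjects rather than in the average. A laboratory summary should therefore count how many subjects got worse and by how much. The one shift scale that the documents define has a ceiling inside the eligible range: once a subject is above 1x ULN, nothing above that point registers. The SAP does not commit even to that table for chemistry or hematology.

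Laboratory evaluation is a named safety endpoint (Protocol 6.4). If a few subjects with raised baselines rose sharply, the laboratory tables would not say how many they were, or whether ALT and bilirubin rose in the same person.

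**Working it through.** The plan gives no figure to reproduce. Two checks and a comparison of the text settle the point.

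**1. What the low-normal-high scale shows.** Inputs: the entry limits in exclusion 9 and the three categories in Protocol 8.2.5.4.2. Rule: a value above 1x ULN is high. The post-dose value of 8x ULN is illustrative.

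| Baseline (x ULN) | Post-dose (x ULN) | Shift shown | Actual change (x ULN) |
|---|---|---|---|
| 0.8 | 8 | normal to high | +7.2 |
| 1.01 | 8 | high to high | +6.99 |
| 2 | 8 | high to high | +6 |
| 3 | 8 | high to high | +5 |

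A rise from a normal baseline is seen. A rise from any baseline above 1x and up to 3x ULN (above 1x and up to 2x for bilirubin) is not.

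**2. What the descriptive statistics show.** Inputs: the statistics in SAP 7 and the planned size of up to about 130 subjects. Assumptions: one subject changes by 8 − 2 = +6x ULN, all others by 0, and N is 100, 110 or 130. Mean change = 6/N.

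| N | Mean change | SD | Median | Maximum |
|---|---|---|---|---|
| 100 | 6/100 = 0.060 | 0.600 | 0 | +6.0 |
| 110 | 6/110 = 0.055 | 0.572 | 0 | +6.0 |
| 130 | 6/130 = 0.046 | 0.526 | 0 | +6.0 |

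The mean and median hide the case. The maximum reveals that it exists, but cannot count:
- With five such subjects among 130, the mean is 30/130 = 0.23 and the maximum is still +6.0.
- If a subject with a normal baseline goes from 0.8x to 8x, the maximum change becomes +7.2 and covers the +6 altogether.

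**3. What the adverse event tables show.** These do count subjects, but three things limit them:
- Reporting depends on the investigator finding the abnormality clinically significant. No numeric trigger appears in the readable text.
- Under Protocol 7.3.2, an abnormality that belongs to a reported syndrome need not be recorded separately.
- Worsening is covered by SAP 12.4, whereas Protocol 6.4 mentions only events that start during or after exposure. The severity descriptions printed in Protocol 7.5 and SAP 14.3 contain no laboratory limits.

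**4. Does the proposed scale register the example?** With bands ≤1x, >1 to 3x and >3x ULN, 2x to 8x moves up a band and is a ratio of 8/2 = 4. A rise from 3x to 8x also moves up a band, with ratio 8/3 = 2.7. Both are counted.

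**The case against.** Most of the case against concerns stronger readings, and it is right about them.

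- **Means only.** A reader might infer that laboratory results are reported as means. They are not: SAP 7 requires the minimum and maximum, which would carry the 8x value and the +6x change.
- **No summary, or listings only.** A reader might infer that such a rise appears in no summary, or only in listings. Protocol 7.3.2 and SAP 14.3 give a planned count by subject for any rise judged clinically significant.
- **A promise withdrawn.** The SAP's sentence on categorical parameters and its listing-only treatment of urinalysis repeat the protocol. The low-normal-high table was promised only where appropriate, and the synopsis leaves a choice between summary statistics and shift tables. The table shells are a separate document (SAP 1) and may contain it. What stands is that SAP 14.5 neither names the table nor defines the categories.
- **Kidney.** Protocol 3.2 says "uptake of OTL0038 in the kidneys is possible", which might be read as a warning of renal injury. Its next sentence says that the imaging will not involve tissue near the kidneys. The passage concerns where the agent localises and does not support that inference.
- **No known signal.** In the Phase 2 lung study (100 subjects, same mg/kg dose; Protocol 3.3.5), events other than the 20 infusion reactions were described as typical of the surgery, and none of the SAEs was attributed to the drug. This makes a hepatic problem less likely, but does not make the scale able to show one.
- **Baseline may differ from screening.** The analysis uses the last value before exposure, and tests are repeated before infusion, so a 2x ULN screening value need not be the baseline. This affects how many subjects are concerned, not whether the scale can register them.

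**Conclusion.** The point holds in a limited form. In the readable text, no planned laboratory table counts subjects whose ALT, AST, ALP or bilirubin worsens from a raised but eligible baseline. Such a rise can be seen as an unattributed maximum, in line listings, or as a TEAE if the investigator judges it clinically significant.

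The number of subjects affected cannot be estimated, because the documents do not say how many would enter above ULN. For a subject who does, the low-normal-high table cannot show any upward change. In the worked example the mean moves by only 0.046x to 0.060x ULN.

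The conclusion assumes that the redacted text and the table shells hold no such table. It is a weakness of reporting: it touches neither the primary analysis nor subject management, and it is not evidence of a liver or kidney effect.

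**What to change.** In SAP 14.5:

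1. State that the protocol's low-normal-high shift table applies to chemistry and hematology, and define which parameters are categorical.
2. For ALT, AST, ALP and total bilirubin, add a shift table of baseline against worst post-baseline value in multiples of ULN. Include the protocol's own entry limits as cut points: for the enzymes ≤1x, >1 to 3x and >3x ULN, with higher bands above; for bilirubin ≤1x, >1 to 2x and >2x ULN.
3. Count subjects who move to a worse band or at least double a raised baseline. Show the two on separate rows, so that a small crossing such as 2.9x to 3.1x is not read as a large rise.
4. Identify subjects with Gilbert's syndrome separately. They may enter above 2x ULN bilirubin and should not count as cases without a change.
5. Cross-tabulate ALT or AST >3x ULN with bilirubin >2x ULN, by subject.
6. If eGFR or creatinine is measured after dosing, summarise it by decline in renal function from baseline, not by the doubling rule.

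If the table shells already contain these tables, a sentence in SAP 14.5 saying so is enough.

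The cost is SAP wording and a few extra descriptive tables. Liver tests are already needed for eligibility, and laboratory assessments are planned before infusion and at Visit 3 (Day 7 ±4). That the Visit 3 panel includes the liver tests is an assumption to confirm. The bands are for reporting only and set no rule for managing subjects.
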